Currently ongoing is the TRAAP 2 trial which started on March 3, 2018, and is expected to be completed in 2020. The targeted sample size is 4,524, in a multicentre double-blind randomized placebo-controlled trial. One gram of TXA or placebo is administered intravenously, slowly over 30 – 60 seconds, after administration of uterotonic, after the cord is clamped, within 3 minutes after birth. The investigators will assess the incidence of PPH (blood loss exceeding 1,000ml) following caesarean delivery (24).

In a local unpublished study conducted at Parirenyatwa and Sally Mugabe Central Hospitals, the pilot to this proposed study, the incidence of PPH was significantly lower in the TXA group compared to the control group in the per protocol analysis. The primary outcome occurred in 37(22.6%) of 164 women who received tranexamic acid and in 90 (31.4%) of the participants who did not receive tranexamic acid (p = 0.021).

There was no significant difference in the intention-to-treat analysis. The results showed a trend towards efficacy of tranexamic acid in preventing postpartum haemorrhage (25).

The available evidence suggests that routine TXA use before caesarean delivery may be a promising drug for the prevention of PPH, decreasing blood loss, and reducing the need for additional uterotonics and product transfusion with very mild adverse effects. However, the safest and most effective dosing, infusion rate, and timing of administration have yet to be determined (4).

JUSTIFICATION

TXA is already widely used in surgery to prevent clot breakdown to reduce blood loss (1). In the third stage of labour to prevent excessive bleeding, there are strong myometrial contractions that are potentiated by oxytocin; increased platelet action; as well as a massive release of coagulation factors with a concurrent increase in fibrinolysis. TXA can counter the fibrinolytic activity thereby facilitating coagulation (17). Its actions would therefore potentiate the effect of uterotonics already in use in reducing blood loss at caesarean section.

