PPH contributes to near-miss cases in addition to actual deaths, due to the serious complications that can occur as a consequence of serious PPH. These include adult respiratory distress syndrome, coagulopathy, shock, loss of fertility, and pituitary necrosis (Sheehan syndrome) (4). If PPH is prevented this could contribute towards reduced hospital stay, avoidance of expensive interventions for intractable PPH (such as hysterectomies and the need for blood products) and conserve our already strained resources.

Prophylactic TXA use has been shown to produce a statistically significant decrease in postpartum blood loss; however, this may not convey clinical significance in terms of transfusion rates and maternal comorbidity from severe haemorrhage. Currently, there is no consensus regarding the optimal timing or dosing of prophylactic TXA for caesarean deliveries (33).

In the light of the above, this research proposes to assess the efficacy of TXA in preventing PPH after caesarean delivery in a population large enough to be adequately powered to add to the current body of evidence. Also, there are no published RCTs, in Southern Africa reporting on TXA in obstetric patients.

GOAL STATEMENT

The aim of this study is to compare the effect of a low dose of TXA (1 g) at the time of skin incision during caesarean delivery together with prophylactic oxytocin administration, versus prophylactic oxytocin alone in an open label randomized clinical trial.

RESEARCH QUESTION

Does intravenous TXA 1g plus Oxytocin 10 IU result in a lower incidence of primary postpartum haemorrhage compared to Oxytocin 10 IU alone after caesarean section?

OBJECTIVES

- 1. To assess the effect of TXA (1g) on postpartum blood loss at caesarean delivery.
- 2. To determine the potential adverse effects of intravenous TXA administered at caesarean section.

PRIMARY OUTCOME

Incidence of PPH, defined by a calculated estimated blood loss > 1000ml or a red blood cell transfusion up to day 2 postpartum

Secondary Outcomes

- Other outcome measures describing postpartum blood loss including
 - o calculated blood loss,
 - visually estimated blood loss,
 - o mean/median number of units of packed red blood cells transfused,
 - o incidence of postpartum shock;
 - o proportion of women requiring supplementary uterotonics,
 - o incidence of postpartum transfusion,
 - o incidence of emergency surgery for PPH including caesarean hysterectomies,

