TXA obtained for the study will be kept in theatre. This is to ensure an uninterrupted supply of the drug for the study. The TXA vials will be kept in theatre in a locked drug cupboard accessible to the researcher and research assistants at the authorization of the sister in charge. A dispensing register for the drugs will be kept together with the drugs. Patient details and study number, amount of TXA dispensed and wasted will be entered into the study register for accountability and to guard against abuse.

Intervention

The participants in the intervention arm will receive generally from the anaesthetist or nurse anaesthetist TXA (1g), administered slowly (over 30 – 60seconds) at the time of skin incision. Participants in both the intervention arm and control group will receive the routine prophylactic 10 IU oxytocin intravenously at birth of the baby. All other aspects of management of the caesarean section will be identical in both arms (34).

Other aspects of the caesarean delivery

- The surgical team will decide on the administration of additional uterotonics and the management of PPH, in a manner consistent with local guidelines. In particular, the use of TXA for the treatment of PPH will be allowed and left to the practitioner's discretion according to the hospital protocol.
- Because the surgeon's level of experience may affect estimated blood loss during or after a caesarean delivery, the obstetrician's experience, categorized as senior resident medical officer, senior house officer, junior registrar, senior registrar or consultant will be recorded (34).

Assessment

Data will be collected and recorded on the data collection tool. Any adverse event will to be reported on the IRB adverse event reporting form.

Primary outcome measure

Estimated blood loss (EBL) will be determined using haematocrit, haemoglobin, and visual estimates.

Calculated estimated blood loss = estimated blood volume \times (preoperative haematocrit – postoperative haematocrit) / preoperative haematocrit. Where estimated blood volume (mL) = weight (kg) \times 85).

The calculation is an objective measure to estimate blood loss because of the inaccuracy of other methods used to determine blood loss and caesarean delivery(35).

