 - iii. sensation of rings or spots of light in visual field
 - iv. dizziness
- c. the occurrence of potential severe adverse effects of TXA during the hospital stay and up to discharge
 - i. deep vein thrombosis, if the diagnosis is confirmed by Doppler ultrasound
 - ii. pulmonary embolism, if the diagnosis is confirmed by radiological examination
 - iii. myocardial infarction
 - iv. seizure
 - v. renal failure requiring dialysis
- d. any other unexpected adverse events

Data Management

The researcher and assistants will allocate each patient codes. No identifiers will be used. Any data collected will be stored in an office accessible only to the researcher and research assistants, as well as on a password-protected laptop computer.

data cleaning and entry

Completed questionnaires will be checked for validity, accuracy and completeness by the principal investigator before data entry into the computer.

Statistical methods and data reporting

Data analysis and reporting will be guided by the Consolidated Standards of Reporting Trials (CONSORT) and will be done by the researchers with the assistance of the statistician. (34).

The women's demographic characteristics and standard risk factors for PPH will be compared between the two groups.

The main analysis of the primary and secondary outcomes will be performed in the modified intention-to-treat (ITT) population, defined as women who undergo randomization and have a caesarean delivery (except if they withdraw consent or are deemed ineligible after randomization).

We will also analyse two separate per-protocol populations: women from the modified ITT population receiving a uterotonic and TXA (as specified in the protocol) (per-protocol group 1); the other will include women from the modified ITT population receiving a uterotonic and then tranexamic acid or no TXA in the 10min after delivery (per-protocol group 2; for a situation more consistent with routine clinical practice). The baseline characteristics of the trial participants, the management of the third stage of labour, and protocol adherence will be compared by descriptive statistics.

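### Per-protocol group 1 admits only women who received TXA, so it has no control arm, and a comparator added later by receipt would be selected on bleeding

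*Combined protocol and SAP*

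**What the plan says.** The section on statistical methods and data reporting gives the main role to the modified ITT set: "The main analysis of the primary and secondary outcomes will be performed in the modified intention-to-treat (ITT) population". It then adds two per-protocol sets. The first consists of modified-ITT women "receiving a uterotonic and TXA (as specified in the protocol) (per-protocol group 1". The second consists of modified-ITT women "receiving a uterotonic and then tranexamic acid or no TXA in the 10min after delivery (per-protocol group 2". The second wording expressly admits women without TXA; the first does not.

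The goal statement describes the comparison as TXA with oxytocin "versus prophylactic oxytocin alone in an open label randomized clinical trial". The Intervention section gives TXA at skin incision to the intervention arm only, and on oxytocin it says: "Participants in both the intervention arm and control group will receive the routine prophylactic 10 IU oxytocin".

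Under other aspects of the caesarean delivery, "the use of TXA for the treatment of PPH will be allowed and left to the practitioner's discretion according to the hospital protocol". This permission is not limited to one arm. Nothing in the plan says how a control woman given treatment TXA is classified in either per-protocol set.

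The literature review reports the pilot's per-protocol result as 37 of 164 women who received TXA (22.6%) against PPH "in 90 (31.4%) of the participants who did not receive tranexamic acid (p = 0.021". It adds that the pilot's intention-to-treat analysis showed no significant difference.

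**The concern.** A per-protocol analysis needs adherent women from both arms. Here adherence in the control arm means not receiving prophylactic TXA, yet group 1 requires TXA. The effect measures promised in the same section (relative risks and absolute risk differences with confidence intervals) therefore have nothing to be computed against in this set.

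Someone will have to supply a comparator at analysis. The obvious choice is women who received no TXA, and the pilot result appears to have been reported that way. But a control woman may receive TXA because she is bleeding, and bleeding is what the primary outcome measures. Sorting on receipt then removes PPH cases from the control side, or adds them to the TXA side.

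An open-label trial should not leave this choice until the data are in hand. In the pilot only the per-protocol analysis was significant, so a per-protocol result may well draw attention again.

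**Working it through.** **Who can enter group 1.** There are two ways to read the qualifier about the protocol.

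- *Strict:* the TXA must be the trial dose at skin incision. Group 1 is then the adherent part of the intervention arm. Control women included: 0 of 581.
- *By receipt:* any TXA counts. The only control women who can enter are those given TXA off allocation, mainly to treat PPH. Adherent control women not given treatment TXA: still 0.

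Neither reading yields a control arm.

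**Inputs for the illustration.** From the sample size section: control rate 5.8%, TXA rate 2.1%, 581 per group, two-sided 5% level, 90% power. The Fleiss formula without continuity correction and with unrounded normal quantiles reproduces 581; the plan's rounded values (1.96 and 1.28) give 579.8. Expected PPH cases are 0.058 × 581 = 33.7 in control and 0.021 × 581 = 12.2 with TXA. The true RR is 0.021 / 0.058 = 0.36.

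**Assumptions.** A share *f* of control PPH cases receives treatment TXA, no other control woman receives any TXA, and every woman in the TXA arm receives TXA. The documents give no value for *f*.

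**Formulas.**

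- Control rate once those women have left: (33.7 − 33.7*f*) / (581 − 33.7*f*).
- (a) Dropped: RR = 0.021 / that rate.
- (b) Counted as TXA: RR = [(12.2 + 33.7*f*) / (581 + 33.7*f*)] / that rate.

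**Results.**

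| *f* | Women affected | Control rate | (a) RR, dropped | TXA rate under (b) | (b) RR, counted as TXA |
|---|---|---|---|---|---|
| 0% | 0 | 5.8% | 0.36 | 2.1% | 0.36 |
| 25% | 8.4 | 4.4% | 0.48 | 3.5% | 0.79 |
| 50% | 16.8 | 3.0% | 0.70 | 4.9% | 1.63 |

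Worked line for *f* = 50%: control (33.7 − 16.8) / (581 − 16.8) = 2.99%; (a) 0.021 / 0.0299 = 0.70; (b) [(12.2 + 16.8) / (581 + 16.8)] / 0.0299 = 0.0486 / 0.0299 = 1.63.

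With no true effect (5.8% in both arms) and *f* = 50%, (a) gives 0.058 / 0.0299 = 1.94 and (b) gives 0.0845 / 0.0299 = 2.83. In this model the bias always runs against TXA.

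**Pilot grouping.** The non-receiver denominator implied by the reported figures is 90 / 0.314 ≈ 287, against 164 receivers. The description is by receipt; the pilot's set is not otherwise defined.

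**Group 2.** Its wording admits untreated women, so it has a comparator. Receipt is judged in the 10 minutes after delivery, so on the natural reading only treatment TXA given within that window can shift a control woman.

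**The case against.** The strongest reply is that the qualifier may be shorthand for TXA or no TXA as allocated. That is probably what was intended. But it is not written, and the same sentence spells out the no-TXA alternative for group 2.

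A reader might infer that group 1 both lacks controls and fills up with control bleeders. The documents do not support both in full at once. Read strictly, the qualifier keeps treatment TXA out of group 1. The sorting then arises only in a comparator built by receipt, which the plan does not specify. This part of the objection stands, and the sorting is therefore stated as conditional.

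A reader might also infer that group 2 is sorted throughout. The 10-minute window prevents that. The primary outcome rests on a day-2 haematocrit or on transfusion up to day 2, and the literature review describes treatment TXA as used where uterotonics fail or trauma is suspected. Much of it may therefore come after the window.

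Nor does the pilot demonstrate the bias. Its per-protocol result favoured TXA, and the bias described here runs the other way. The pilot shows only that reporting by receipt is a realistic possibility. Its rates should not be used as true rates for this calculation, since they may already be affected by such grouping.

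The values of *f* have no source. Clinicians also treat on bedside bleeding, so some treated control women would not meet the primary outcome. Removing or moving them as well would offset part of the bias.

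Finally, the plan gives the per-protocol sets no decision role. That stands, and it limits the severity.

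**Conclusion.** Per-protocol group 1 cannot deliver a comparison as written. This follows from the text alone and needs no assumption about rescue use.

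The bias from a receipt-based comparator is a conditional risk. At the plan's rates it would move an RR of 0.36 to 0.48 or 0.70 if the treated control cases are dropped, and to 0.79 or 1.63 if they are counted as TXA, for *f* of 25% or 50%. These figures rest on assumed shares and on treatment TXA going only to control women who meet the primary outcome. For group 2 the relevant share is the one treated within 10 minutes of delivery, which may be much smaller.

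A reader might conclude that the trial's main result is compromised. It is not: the modified ITT analysis is primary, and the 581 per group does not depend on these sets. This should be fixed, as a defect in a supportive analysis.

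**What to change.** Define the per-protocol sets by randomised arm and prophylactic treatment only.

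- **TXA arm:** allocated to TXA, and received the protocol TXA and the routine oxytocin.
- **Control arm:** allocated to control, and received the routine oxytocin and no prophylactic TXA.

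Add one sentence: TXA given to treat PPH neither excludes a woman nor changes her arm, in any per-protocol set. Under the model above, membership then no longer depends on *f*, and the comparison returns to about 12 vs 34 expected cases (RR 0.36), before other deviations.

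Make sure the data form records the purpose (prophylaxis or treatment) and time of every TXA dose. The form is not in the documents and may already do this. The pharmacy plan's register logs study TXA by study number, but the plan does not say whether it covers treatment doses. The field has to be in place before data collection, because purpose and timing may not be recoverable later.

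The cost is a few lines of analysis-plan wording and, if missing, one form field. It needs no extra participants and no change to care. While editing, also reconcile group 2, which places TXA after the uterotonic, with the Intervention section, which places it at skin incision; that is a separate point.

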Study Setting

The study will be performed at two tertiary institutions that are affiliated to the University of Zimbabwe that serve as referral centres for clinics located in Harare as well as district and provincial hospitals in the surrounding provinces: Sally Mugabe Central Hospital Maternity Unit and Parirenyatwa Group of Hospitals i.e. Mbuya Nehanda Maternity Hospital (MNMH). Most of these patients understand both English and Shona languages.

Sample size

The sample size has been calculated assuming a proportion of 2.1% PPH in the experimental group and 5.8% (34) in the control group at 95% confidence interval and 90% power using the Fleiss formula giving a minimum sample size of

$$n = \frac{\left[\frac{Z_{\alpha}\sqrt{(r+1)\overline{p}\overline{q}} + Z_{\beta}\sqrt{rp_{1}q_{1} + p_{2}q_{2}}\right]^{2}}{r(p_{1} - p_{2})^{2}}$$

$$n = \frac{\left[\frac{1.96\sqrt{(1+1) \times 0.0395 \times 0.9605} + 1.28\sqrt{0.021 \times 0.979 + 0.058 \times 0.942}\right]^{2}}{(0.021 - 0.058)^{2}}$$

= 581 per group

Thus, total minimum sample size N = 1, 162 women

Where: n = sample size

 Z_{α} = 1.96 at 95% confidence interval

```
\alpha = probability of a type I error (significance level) = 0.05 \beta = probability of a type II error (1 – power of test)
```

 p_1 = proportion of PPH in the experimental group = 0.021

 p_2 = proportion of PPH in the control group = 0.058

r = ratio of control group/population 2 to experimental group/population 1

q = 1-p

Randomization

A randomized allocation to study and control groups using computer-generated random numbers will be prepared by the trial statistician.

Pharmacy Plan

Oxytocin iv is dispensed weekly from the pharmacy to theatre, where it is stored in a refrigerator in the custody of the sister in charge. All patients undergoing caesarean delivery routinely receive 10IU oxytocin iv, administered slowly by the anaesthetist after delivery of baby at Sally Mugabe Hospital Maternity Unit and Mbuya Nehanda Maternity Hospital. Cold chain will be maintained up to the administration of drug to the patient.

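### Per-protocol group 2 is worded for a uterotonic-then-TXA sequence, but this trial gives TXA at skin incision and oxytocin at or after birth

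*Combined protocol and SAP*

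**What the plan says.** All references are to the combined protocol and SAP.

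- **Statistical methods and data reporting.** The main analysis uses the modified ITT population, and two per-protocol populations are added. Group 1 is women "receiving a uterotonic and TXA (as specified in the protocol) (per-protocol group 1"). Group 2 is women "receiving a uterotonic and then tranexamic acid or no TXA in the 10min after delivery", and its stated aim is "for a situation more consistent with routine clinical practice". The section does not say whether group 2 is then compared by allocated arm or by TXA received.
- **Goal Statement.** TXA is given "at the time of skin incision during caesarean delivery together with prophylactic oxytocin administration". The Intervention section also puts TXA at skin incision.
- **Intervention.** Women in both arms "will receive the routine prophylactic 10 IU oxytocin intravenously at birth of the baby".
- **Pharmacy Plan.** "All patients undergoing caesarean delivery routinely receive 10IU oxytocin iv, administered slowly by the anaesthetist after delivery of baby".
- **Other aspects of the caesarean delivery.** Separately from the randomised dose, "the use of TXA for the treatment of PPH will be allowed", at the practitioner's discretion.

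**The concern.** A per-protocol definition should pick out women treated as the protocol describes. The TXA limb of group 2 instead describes a sequence that the protocol does not plan in either arm. Two consequences follow.

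First, an analyst cannot build group 2 without decisions that the text does not make: whether to enforce the order, what the 10 minutes refer to, and whether the two limbs define membership only or also exposure. Two analysts could produce different sets.

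Second, the only TXA the protocol foresees after delivery is treatment for PPH. If that TXA qualifies a woman for the TXA limb, she is there because she bled, and bleeding is the primary outcome.

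The choice of population is not idle in this programme. The Literature review reports that the pilot found lower PPH with TXA in the per-protocol analysis (22.6% against 31.4%, p = 0.021) and no significant difference by intention to treat. The present trial is open-label, so membership rules settled after the data are seen would be hard to defend.

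**Working it through.** The plan gives no figure for group 2, so the check is a comparison of sections.

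**Step 1: order of events.**

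| Source | TXA | Uterotonic |
|---|---|---|
| Goal Statement | at skin incision | no separate time given |
| Intervention | at skin incision | at birth |
| Pharmacy Plan (oxytocin) | not timed | after delivery |
| Per-protocol group 2, TXA limb | after the uterotonic | before TXA |

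Skin incision precedes birth, so the dosing sections give TXA, then delivery, then oxytocin. The Goal Statement couples the two drugs, but the Intervention section times them separately, and neither puts oxytocin first. The group 2 order is the reverse, and no section resolves the difference.

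**Step 2: who enters under each reading.** Assume every woman receives oxytocin within 10 minutes of delivery.

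| Woman | (a) Order kept; window applies to both limbs | (b) Order kept; window applies to the no-TXA limb only | (c) Order kept; window times the uterotonic, and no TXA means none at all | (d) Order ignored; window times the uterotonic |
|---|---|---|---|---|
| TXA arm, dosed at incision, no more TXA | no-TXA limb only | no-TXA limb only | neither limb | TXA limb |
| Control, no TXA | no-TXA limb | no-TXA limb | no-TXA limb | no-TXA limb |
| Either arm, TXA after oxytocin and within 10 minutes (late dose or treatment) | TXA limb | TXA limb | TXA limb | TXA limb |
| TXA arm, TXA never given | no-TXA limb | no-TXA limb | no-TXA limb | no-TXA limb |

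Under every reading that keeps the order, the correctly treated woman fails the TXA limb. Under (a) she fails on timing as well. Only (d) puts her there, and (d) requires a word of the definition to be disregarded.

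**Step 3: effect on exposure.** If the limbs also define exposure, readings (a) and (b) count correctly treated women as untreated. Under all four readings, a control given treatment TXA within 10 minutes counts as TXA-treated. If the limbs define membership only and the comparison is by allocated arm, neither misclassification occurs.

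**Step 4: what is untouched.** The modified ITT definition does not refer to TXA receipt or timing. Group 1 states no order and points to the protocol's own regimen. The sample size does not use the definition. With the plan's rounded z values,

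[1.96√(2 × 0.0395 × 0.9605) + 1.28√(0.021 × 0.979 + 0.058 × 0.942)]² / (0.037)² = 579.8,

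and unrounded z values give the stated 581 per group.

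**The case against.** The strongest reply is that group 2 can still be built. Its second limb admits women with no TXA in the 10 minutes after delivery, and a woman dosed at incision with no further TXA literally satisfies it. The text describes who is in the population and does not say that the limbs define exposure. The comparison could then be by allocated arm, with correctly treated women present on both sides and a relative risk available. The word *then* may also be a slip. In any case this is one supportive population.

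Most of this stands. A reader might infer from the order mismatch that none of the planned 581 TXA-arm women could be in group 2, so that its TXA arm would be empty. The documents do not support that, because the second limb is open to them under two of the readings above and the TXA limb under a third.

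The reply does not rescue the wording. Treated women would qualify through the limb meant for the untreated. A TXA-arm woman who never received TXA would enter by the same limb, so the definition would not separate adherent from non-adherent women. Comparison by allocated arm is a reasonable choice, but the plan does not state it.

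**Conclusion.** The wording conflict is certain: the group 2 definition assumes an order opposite to that of the Goal Statement, Pharmacy Plan and Intervention sections. A TXA-arm woman treated as specified does not meet its TXA limb, while a woman given TXA after delivery, including for treatment, could. This should be fixed.

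The size cannot be stated. The documents give no rate for late or treatment TXA, and the effect depends on which reading the analyst adopts. Selection on the outcome is a risk under the literal wording, not an established bias. It would misclassify exposure only if the limbs, not the allocated arm, define it. The damage is confined to group 2.

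Three further inferences are tempting and should not be drawn:

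- **That the definition was carried over from the cited placebo-controlled trial at caesarean delivery.** The order matches the Literature review's description of that trial. However, the interval given there is 3 minutes, not 10, and its per-protocol definitions are not given.
- **That group 1 has no control criterion.** Its reference to the protocol can be read as receipt of the allocated regimen.
- **That drug times will not be recorded.** The TXA register entry reads "Patient details and study number, amount of TXA dispensed and wasted will be entered into the study register", but that register serves drug accountability. The data collection tool is not shown, and the plan to compare protocol adherence implies that some administration data will be collected.

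**What to change.** Before analysis, reconcile the group 2 definition in the Statistical methods section with the Goal Statement, Pharmacy Plan and Intervention sections:

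1. Remove the requirement that the uterotonic comes first.
2. State that group 2 is compared by allocated arm, with a membership criterion for each arm.
3. If the 10-minute window is kept, say which drug and which event it refers to, in terms of this trial's own administration times.
4. Keep group 2 distinct from group 1. Group 1 is the regimen as specified; group 2 should be the broader routine-practice set, with the departures it tolerates named in advance by the investigators. Restating the specified regimen by arm would only reproduce group 1.
5. State that TXA given to treat PPH neither qualifies nor disqualifies a woman and does not change her exposure group.

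The cost is a wording change in one section. Applying it needs the times of TXA and oxytocin and the reason TXA was given, where these are collected. Whether the data collection tool already holds them cannot be judged from the documents, so the team should check. No dose, drug timing or treatment rule needs to change for this correction, and neither do the main analysis or the sample size.
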